#### For subjects in the CSF sub-study:

- MRI should be performed and results available prior to LP.
- LPs should be performed via gravity drip method with atraumatic needles to reduce the risk of CSF leakage and post-LP headaches. This technique will allow for optimal biomarker collection and analysis.
- Site should schedule the LP as soon as possible, no later than 2 weeks after the MRI.
- CSF sample collection for biomarker assessment (exact time will be recorded)
- CSF sample collection for PK assessment (exact time will be recorded)

#### 7.2.15. Retrieved Dropout Visit

In addition to the ET visit, subjects who discontinue the study drug during the trial will be encouraged to remain in the study (off study drug) for continued RDO visits by attending Week 52 (if applicable) and Week 78 (EOT) visits. The RDO visits will include the following procedures, in the recommended order shown below:

- Vital signs
- AE assessment
- Change in medications since last visit
- ADAS-Cog
- A-IADL
- MMSE
- NPI

For subjects who prematurely withdraw from the study,, they will be encouraged to return at Week 78 to finish study-related procedures.

#### 7.2.16. Unscheduled Visit

Unscheduled Visit, at the discretion of the Investigator, may occur at any time, and appropriate procedures and evaluations will be conducted and documented in the eCRF.

#### 8. ADVERSE EVENTS

# 8.1. Specification of Safety Parameters

All of the following safety endpoints will be recorded on the eCRF.

• Occurrence and severity of TEAEs and SAEs

Confidential Page 79 of 115

- Occurrence of clinically significant abnormal findings in laboratory tests, as determined by the Investigator
- Occurrence of clinically significant abnormal findings in ECG, as determined by the central ECG reader
- Occurrence of abnormal findings in physical examination, including weight and vital signs (pulse rate, body temperature, respiratory rate, and BP)
- Occurrence of abnormal findings in MRI central readings for ARIA-E or ARIA-H
- Occurrence of abnormal findings in C-SSRS
- Pregnancy for females of childbearing potential

#### 8.1.1. Definition of Adverse Event (AE)

**Adverse Event**: An AE is any untoward medical event that occurs in a subject or clinical investigation subject administered a pharmaceutical product, and which does not necessarily have to have a causal relationship with this treatment. An AE can therefore be any unfavorable and unintended sign (including clinically significant abnormal laboratory findings), symptom, or disease temporally associated with the use of an investigational product, whether or not considered related to the product. Examples include the following:

- Any treatment-emergent signs and symptoms (events that are marked by a change from the subject's baseline/entry status [e.g., an increase in severity or frequency of pre-existing abnormality or disorder]);
- All reactions from study drug, abuse of drug, withdrawal phenomena, sensitivity, or toxicity to study drug;
- Apparently unrelated illnesses;
- Injury or accidents;
- Exacerbations of the underlying disease (indication);
- Extensions or exacerbations of symptomatology, subjective events reported by the study subject, new clinically significant abnormalities in clinical laboratory, physiological testing, or physical examination.

The following is not considered an AE:

- Elective procedure unless related to the AD diagnosis
- Pre-existing conditions found as a result of screening procedures

**Treatment-emergent Adverse Event:** A TEAE is defined as any new AE that begins, or any preexisting condition that worsens in severity, after at least one dose of study treatment has been administered.

Confidential Page 80 of 115

#### 8.1.2. Definition of Serious Adverse Event (SAE)

**Serious Adverse Event:** An SAE is defined as any untoward medical event that results in any of the following outcomes:

- Death
- A life-threatening AE

**Note:** This means that the subject is at immediate risk of death at the time of the event; it does not mean that the event hypothetically may have caused death if it were more severe.

- Inpatient hospitalization or prolongation of existing hospitalization
  - O Hospitalization is defined by the Sponsor as a full admission to the hospital for diagnosis and treatment. This includes prolongation of an existing inpatient hospitalization. Hospitalization may include social hospitalization, defined as inadequate family support or care at the study subject's primary residence that results in the study subject being admitted to the hospital (i.e., wound care, nutrition).
  - Exceptions: Emergency Room visits that do not result in a hospital admission; outpatient surgery; preplanned or elective procedures; and/or protocol procedures. These events would not be reported as SAEs unless the event triggering the hospital visit is an SAE as defined by other SAE criteria such as life-threatening, resulting in disability or incapacity, or per the medical judgment of the Investigator.
  - Any other event fulfilling the definition of serious that develops as a result of the in-hospital procedure or extends the hospital stay is an SAE.
- A persistent or significant disability or incapacity or substantial disruption of the ability to conduct normal life functions
  - O Disability is defined as a substantial disruption in a person's ability to conduct normal life functions.
- A congenital anomaly or birth defect
- Important medical event(s)
  - o Important medical events that may not result in death, be life-threatening, or require hospitalization may be considered serious when, based upon appropriate medical judgment, they may jeopardize the patient or subject and may require medical or surgical intervention to prevent one of the outcomes listed in this definition.

**Pregnancy**: In addition, and for the purposes of monitoring, the following should be reported via the Pregnancy eCRFs, as appropriate, according to the instructions provided in [Section 8.4.3].

- Any occurrence of pregnancy of female study subjects or female sexual partners of male study subjects (with or without AEs).
- Any study subject who becomes pregnant during the study must be withdrawn from treatment and will be followed to term and/or other pregnancy outcome.
- For all female study subjects, a serum pregnancy test must be performed at the Screening Part 2 Visit.

Confidential Page 81 of 115

- Females of non-childbearing potential are defined as follows:
  - o Be postmenopausal with amenorrhea for at least 1 year prior to the first dose and FSH serum levels consistent with postmenopausal status, or
  - O Have undergone one of the following documented sterilization procedures at least 6 months prior to the first dose:
    - hysteroscopic sterilization,
    - bilateral tubal ligation or bilateral salpingectomy,
    - hysterectomy, or
    - bilateral oophorectomy.
- Females of childbearing potential, defined as a premenopausal female capable of becoming pregnant, will be included if they are either sexually inactive (sexually abstinent for 14 days prior to the first dose and confirm to continue through 28 days after the last dose) or using one of the following highly effective contraceptives (i.e., results in < 1% failure rate when used consistently and correctly) 14 days prior to the first dose continuing through 28 days after the last dose:
  - o IUD,
  - o surgical sterilization of the partner (vasectomy for 6 months minimum),
  - o combined (estrogen or progestogen containing) hormonal contraception associated with the inhibition of ovulation (either oral, intravaginal, or transdermal),
  - o progestogen only hormonal contraception associated with the inhibition of ovulation (either oral, injectable, or implantable),
  - o IUS, or
  - o bilateral tubal occlusion.

#### 8.1.3. Definition of Unanticipated Problems

The Office of Human Research Protection (OHRP) considers unanticipated problems (UPs) involving risks to participants or others to include, in general, any incident, experience, or outcome that meets all of the following criteria:

- Unexpected in terms of nature, severity, or frequency given (a) the research procedures that are described in the protocol-related documents, such as the IRB-approved research protocol and ICF; and (b) the characteristics of the participant population being studied
- Related to participation in the research
- Research placing participants or others at a greater risk of harm (including physical, psychological, economic, or social harm) than was previously known or recognized

This study will use the OHRP definition of UPs.

Confidential Page 82 of 115

#### 8.2. Classification of an Adverse Event

#### 8.2.1. Severity of Event

Investigators should assess the severity of AEs according to the National Cancer Institute CTCAE version 5.0. In general, CTCAE severity grades are defined as follows:

- Grade 1: Mild; asymptomatic or mild symptoms; clinical or diagnostic observations only; intervention not indicated.
- Grade 2: Moderate; minimal, local or noninvasive intervention indicated; limiting age-appropriate instrumental ADL. Instrumental ADL refer to preparing meals, shopping for groceries or clothes, using the telephone, managing money, etc.
- Grade 3: Severe or medically significant but not immediately life-threatening; hospitalization or prolongation of hospitalization indicated; disabling; limiting self-care ADL. Self-care ADL refer to bathing, dressing and undressing, feeding self, using the toilet, taking medications, and not bedridden.
- Grade 4: Life-threatening consequences; urgent intervention indicated.
- Grade 5: Death related to AE.

These five categories are based on the Investigator's clinical judgment, which in turn depends on consideration of various factors such as the study subject's reports, the physician's observations, and the physician's prior experience. The severity of the AE should be recorded in the appropriate section of the eCRF. The evaluation of severity is distinguished from the evaluation of "seriousness." A severe event may not meet the criteria for seriousness and a serious event may be evaluated as mild.

### 8.2.2. Causality

The following should be considered when assessing causality:

- temporal associations between the agent and the event;
- cessation or rechallenge;
- compatibility with known class effect;
- known effects of concomitant medications;
- pre-existing risk factors;
- a plausible mechanism; and
- concurrent illnesses.

The Investigator will assess the causality/relationship between the study drug and the AE. One of the following categories should be selected based on medical judgment, considering the definitions and all contributing factors:

Categories of attribution for "Related"

• Definitely related: There is clear evidence to suggest a causal relationship, and other possible contributing factors can be ruled out.

Confidential Page 83 of 115

• Possibly related: There is some evidence to suggest a causal relationship (e.g., the event occurred within a reasonable time after administration of the study drug). However, the influence of other factors may have contributed to the event (e.g., the study subject's clinical condition, other concomitant events).

Categories of attribution for "Unrelated"

- Unlikely to be related: There is little evidence to suggest there is a causal relationship. There is another reasonable explanation for the event.
- Not related: An AE will be considered "not related" to the use of the product if any of the following tests are met:
  - O An unreasonable temporal relationship exists between administration of the product and the onset of the AE (e.g., the event occurred either before or too long after administration of the product for it to be considered product related).
  - A causal relationship between the product and the AE is biologically implausible (e.g., death as a passenger in an automobile accident).
  - A clearly more likely alternative explanation for the AE is present (e.g., typical adverse reaction to a concomitant drug and/or typical disease-related event).

#### 8.2.3. Expectedness

Sponsor will be responsible for determining whether an SAE is expected or unexpected. An SAE will be considered unexpected if the nature, severity, or frequency of the event is not consistent with the risk information described in the Investigator's Brochure.

# 8.3. Time Period and Frequency for Event Assessment and Follow-up

The occurrence of an AE or SAE may come to the attention of study personnel during study visits and interviews of a study participant presenting for medical care, or upon review by a study monitor. All AEs including local and systemic reactions not meeting the criteria for SAEs will be captured on the appropriate eCRF. Information to be collected includes event description, dates and times of onset and resolution, clinician's assessment of severity, assessment of relatedness to study drug (assessed only by those with the training and authority to make a diagnosis), and action taken. All AEs occurring while on study must be documented appropriately regardless of relationship.

Any medical condition that is present at the time that the participant is screened will be considered as baseline and not reported as an AE. However, if the study participant's condition deteriorates at any time during the study, it will be recorded as an AE. UPs will be recorded in the data collection system throughout the study.

Changes in the severity of an AE will be documented to allow an assessment of the duration of the event at each level of severity to be performed. AEs characterized as intermittent require documentation of onset and duration of each episode.

The Investigator or designee will record all reportable events with start dates occurring any time after informed consent is obtained until the AE has resolved, stabilized, or a new chronic baseline has been established. At each study visit, the Investigator or designee will inquire about the

Confidential Page 84 of 115

occurrence of AE/SAEs since the last visit. Events will be followed for outcome information until resolution or stabilization.

# 8.4. Collecting, Reporting, and Recording Procedures

### 8.4.1. Collecting, Reporting, and Recording Adverse Events

All AEs will be collected and recorded in the eCRF for each subject from the day of signed ICF until the end of Safety Follow-up Visit. All AEs regardless of relatedness to the study drug, must be fully and completely documented on the AE eCRF and in the subject's medical notes. AEs may be volunteered spontaneously by the study subject or discovered by the study staff during physical and neurological examinations or by asking an open-ended non-leading question such as: "How have you been feeling since you were last asked?" The Investigator will document the nature of AE, date of onset of the AE (and time, if known), date of outcome of the AE (and time, if known), severity of the AE, action taken with study drug as a result of the AE, assessment of the seriousness of the AE, and assessment of the causal relationship of the AE to study drug and/or study procedure. All AEs experienced by a subject, irrespective of the suspected causality, will be monitored until the AE has resolved, stabilized, or a new chronic baseline has been established, abnormal laboratory values have returned to baseline or normal levels, there is a satisfactory explanation for the changes observed, the subject is lost to follow-up, or the subject has died.

All AEs should be recorded individually in the subject's own words (verbatim) unless, in the opinion of the Investigator, the AEs constitute components of a recognized condition, disease, or syndrome. In the latter case, the condition, disease, or syndrome should be named rather than each individual symptom.

Concomitant illnesses that existed before entry into the study will not be considered an AE unless the illness worsens during the treatment period. Pre-existing conditions will be recorded in the eCRF on the Medical History or appropriate page as well as on the SAE Report Form (Medical History section).

#### 8.4.2. Collecting, Reporting, and Recording Serious Adverse Events

In addition to the severity rating, each AE is to be classified by the Investigator as "serious" or "not serious." The seriousness of an event is defined according to the applicable regulations and generally refers to the outcome of an event. An SAE is one that meets one or more of the criteria listed in [Section 8.2.1].

The reporting of SAEs by the Sponsor to the Regulatory Authorities is a regulatory requirement. Each Regulatory Authority has established a timetable for reporting SAEs based upon established criteria. It is the responsibility of the principal Investigator to report to the Pharmacovigilance and Safety Services group and to document the SAE in the eCRF within 24 hours of learning of occurrence.

The SAE (initial and/or follow-up) must be reported by completing the SAE eCRFs, as appropriate (refer to the eCRF Completion Guidelines for details). Calls related to fatal/life-threatening SAEs should first be directed to the Medical Monitor (refer to the contact list in this protocol for contact information). If the Medical Monitor is not available, please contact the Sponsor Medical Officer.

Confidential Page 85 of 115

Suspected Unexpected Serious Adverse Reaction (SUSAR) is the term used to refer to a serious adverse event that occurs in a clinical trial subject, which is assessed by the Sponsor as being unexpected and having a reasonable possibility of a causal relationship with the study drug (adverse reaction). Reports of these reactions are subject to expedited submission to health authorities.

SAEs are to be reported via the electronic data capture (EDC) system when it is available the SAE eCRFs are to be completed with all the current information (refer to the eCRF Completion Guidelines for details).

If the EDC system is unavailable, SAEs can be reported on a paper form. This form (for initial and/or follow-up information) and cover sheet will include all available supporting documentation relevant to the event. This form is to be emailed (within 24 hours of discovery) to the following:

SAE REPORTING CONTACT INFORMATION
Department: Pharmacovigilance and Safety Services
Company:
Email address:
Telephone:
Fax:

After the initial AE/SAE report, the Investigator is required to proactively follow each subject at subsequent visits and phone contacts. All SAEs will be followed until resolution, stabilization, the event is otherwise explained, or the subject is lost to follow-up. In the event of any SAE (other than death), the study subject will be instructed to contact the Investigator (or designee) using the telephone number provided in the ICF. All study subjects experiencing an SAE will be seen by the Investigator or designee as soon as is feasible following the report of the SAE.

All SAEs will continue to be followed until the end of the study or until such events have resolved or the Investigator, in conjunction with the Sponsor, deems them to be chronic or stable.

SAEs occurring up to the safety follow-up visit should be reported.

### 8.4.3. Collecting, Reporting, and Recording Pregnancy

Females of childbearing potential will be required to take pregnancy test before IMP administration. The results of the pregnancy testing must be negative in order to be in the study.

- Females of non-childbearing potential are defined as follows:
  - o Be postmenopausal with amenorrhea for at least 1 year prior to the first dose and FSH serum levels consistent with postmenopausal status, or
  - O Have undergone one of the following documented sterilization procedures at least 6 months prior to the first dose:
    - hysteroscopic sterilization,
    - bilateral tubal ligation or bilateral salpingectomy,

Confidential Page 86 of 115

- hysterectomy, or
- bilateral oophorectomy.
- Females of childbearing potential, defined as a premenopausal female capable of becoming pregnant, will be included if they are either sexually inactive (sexually abstinent for 14 days prior to the first dose and confirm to continue through 28 days after the last dose) or using one of the following highly effective contraceptives (i.e., results in < 1% failure rate when used consistently and correctly) 14 days prior to the first dose continuing through 28 days after the last dose:
  - o IUD,
  - o surgical sterilization of the partner (vasectomy for 6 months minimum),
  - o combined (estrogen or progestogen containing) hormonal contraception associated with the inhibition of ovulation (either oral, intravaginal, or transdermal),
  - o progestogen only hormonal contraception associated with the inhibition of ovulation (either oral, injectable, or implantable),
  - o IUS, or
  - o bilateral tubal occlusion.

In the event that a female subject or a male subject whose female partner does become pregnant at any time through 28 days after the last dose, the Investigator must notify the Medical Monitor or designee within 48 hours of learning about the pregnancy. Any study subject that becomes pregnant during the study must be withdrawn from treatment and will be followed to term and/or other pregnancy outcome.

The Investigator will be required to complete the Pregnancy Report/Outcome Form and any additional documents provided by the Sponsor, follow the subject through the pregnancy term, and report to the Medical Monitor or designee the course of the pregnancy, including perinatal or neonatal outcome.

Information on the status of the mother and the child will be forwarded to the Medical Monitor or designee using the Pregnancy Report/Outcome Form. Any premature termination of the pregnancy will also be reported on this form.

Although pregnancy occurring in a clinical study is not considered to be an SAE, any pregnancy complication or elective termination of a pregnancy for medical reasons will be recorded as an AE and will be followed as such. A spontaneous abortion is considered to be an SAE.

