#### OR

• If of childbearing potential, defined as a premenopausal female capable of becoming pregnant, must also have negative serum and urine pregnancy results prior to dosing, and either sexually inactive (sexually abstinent for 14 days prior to the first dose continuing through 28 days after the last dose) or use a highly effective method of contraception (with a failure rate of less than 1% per year when used consistently and correctly) 14 days prior to the first dose continuing through 28 days after the last dose.

**Note:** Highly effective methods include the following:

- intrauterine device (IUD),
- surgical sterilization of the partner (vasectomy for 6 months minimum),
- combined (estrogen or progestogen containing) hormonal contraception associated with the inhibition of ovulation (either oral, intravaginal, or transdermal),
- progestogen only hormonal contraception associated with the inhibition of ovulation (either oral, injectable, or implantable),
- intrauterine hormone-releasing system (IUS), or
- bilateral tubal occlusion.

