#### 19. If male,

EITHER be non-vasectomized and agrees to use a condom with spermicide or abstain from sexual intercourse during the study until 90 days after the last dose of study medication and the female partner agrees to inclusion criterion 18,

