#### OR

be vasectomized at least 6 months prior to first dose and agrees to use a condom during sexual intercourse, or less than 6 months prior to first dose and must follow the same restrictions as a non-vasectomized male.

- 20. If treated with an AChEI, must be on a stable treatment for at least 12 weeks prior to the Baseline Visit and must be able to continue on the same drug for the duration of the study.
- 21. If treated with permitted antidepressants, mood stabilizers, or other psychotropic medications, must be on a stable dose according to [Table 1]. Only two anticonvulsants are permitted (for any use) as indicated in Table 1.
- 22. If taking permitted, non-psychotropic medications for the treatment of non-excluded medical conditions, must be on a stable dose according to [Table 1].

Confidential Page 43 of 115

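### Partner pregnancies on Days 29–90 after a male subject's last dose are not clearly required to be notified, although the male contraception rule runs to Day 90.

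*Protocol*

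**What the plan says.** Four places in the protocol bear on this. The SAP does not address pregnancy reporting.

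- **Section 5.1, criterion 19 (men).** A non-vasectomized man agrees to use a condom with spermicide or to "abstain from sexual intercourse during the study until 90 days after the last dose of study medication". A man vasectomized less than 6 months before first dose "must follow the same restrictions as a non-vasectomized male". A man in the remaining group must "be vasectomized at least 6 months prior to first dose and agrees to use a condom during sexual intercourse"; no end date is given for that duty. For the non-vasectomized man, the female partner must also agree to criterion 18.
- **Section 5.1, criterion 18 (women of childbearing potential).** Abstinence or highly effective contraception is required from "14 days prior to the first dose continuing through 28 days after the last dose".
- **Section 8.1.2, Pregnancy.** The events to be reported are "Any occurrence of pregnancy of female study subjects or female sexual partners of male study subjects (with or without AEs"). The sentence has no time limit. It sends these reports through the pregnancy case report forms under the instructions of Section 8.4.3.
- **Section 8.4.3.** The investigator must notify the Medical Monitor or designee, within 48 hours of learning of it, when a female subject, or the partner of a male subject, "does become pregnant at any time through 28 days after the last dose". The same section then provides for the outcome form and for reporting of the perinatal or neonatal outcome.

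**The concern.** The 28 days in Section 8.4.3 equal the contraception period for female subjects in criterion 18. The section applies that number to partners of male subjects as well, although criterion 19 sets a longer period for most men. No separate reporting period for partners appears anywhere.

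Reports of pregnancy after possible exposure are safety data on an investigational drug. The protocol treats them that way: Section 8.4.3 records pregnancy complications as adverse events and spontaneous abortion as a serious adverse event. That process starts with notification. If a site takes 28 days as the limit, a partner pregnancy that begins later does not start it, even though the man was still under the protocol's own contraception rule.

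**Working it through.** The plan gives no figure to reproduce. The check compares the windows and the visit calendar.

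**Inputs**

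| Item | Value | Source |
|---|---|---|
| Male contraception, non-vasectomized or vasectomized < 6 months before first dose | to Day 90 after last dose | Protocol 5.1, criterion 19 |
| Male contraception, vasectomized ≥ 6 months before first dose | condom, no end date | Protocol 5.1, criterion 19 |
| Contraception, women of childbearing potential, and partners through criterion 19 | to Day 28 after last dose | Protocol 5.1, criterion 18 |
| Notification window, subject or partner | to Day 28 after last dose | Protocol 8.4.3 |
| General reporting statement | no limit of its own; refers to 8.4.3 | Protocol 8.1.2 |
| Last dose, completers | Week 78, Day 547 ± 14 | Protocol 7.2.12 and Appendix 2 |
| Last scheduled visit | Week 82, Day 574 ± 7 | Protocol 7.2.13 and Appendix 2 |

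**Step 1: length of the gap.** 90 − 28 = 62 days, that is Days 29 to 90 after the last dose.

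**Step 2: does the last visit reach it?** Nominally 574 − 547 = 27 days after the last dose, which is before Day 29. Taking the two visit windows independently:

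- Week 78: Day 547 − 14 = 533 to Day 547 + 14 = 561.
- Week 82: Day 574 − 7 = 567 to Day 574 + 7 = 581.
- Shortest interval: 567 − 561 = 6 days. Longest: 581 − 533 = 48 days.

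Even at the longest interval, 90 − 48 = 42 days of the male contraception period follow the last scheduled contact. Sections 8.4.1 and 8.4.2 collect adverse events and serious adverse events up to this visit, so general safety collection does not extend past it for new events.

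**Step 3: does Section 8.1.2 close the gap?** It can be read in two ways. Either it defines what is reportable, without limit, and Section 8.4.3 adds the 48-hour rule for pregnancies through Day 28; or, because it defers to Section 8.4.3, the 28 days limit the whole duty. The text does not settle which.

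**Step 4: which pregnancies are affected?** Section 8.4.3 counts its 48 hours from when the investigator learns of the pregnancy. A conception by Day 28 that is discovered later therefore remains notifiable. Only pregnancies beginning on Days 29–90 are in doubt.

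**The case against.** A reader might infer that partner pregnancies in the last two months of the contraception period go unreported, that the passages contradict one another, and that the protocol itself calls 90 days its risk period. The documents do not support those stronger statements.

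- **Unreported.** Section 8.1.2 can fairly be read as requiring a report at any time, and Section 8.4.3 does not forbid later reports. What is missing is a clear duty.
- **Contradiction.** Criterion 19 governs what the man agrees to do; Section 8.4.3 governs when the investigator must notify. Both can be obeyed in full. Within criterion 19, the man's 90 days and the partner's 28 days add to each other. The direct tension is between the unlimited wording of Section 8.1.2 and the 28 days of Section 8.4.3.
- **Risk period.** Criterion 19 gives no reason for 90 days and does not use that term. A precaution period can be set longer than a reporting period on purpose, but nothing in the documents says that this was done.
- **All male subjects.** The 90-day limit is explicit only for the two groups named above.
- **A large share.** 62/90 = 69% is a proportion of calendar days. It says nothing about the number of pregnancies.

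Three further limits are fair. SAP Section 3.2 lets eligible completers enter a long-term extension study, possibly without the Week 82 visit; reporting for those men may fall under that study's protocol, which is not among the documents. The eCRF Completion Guidelines, the Safety Management Plan and other sponsor documents that the protocol mentions may address later partner pregnancies, and they cannot be checked here. Finally, few events are likely with subjects aged 50 to 80, although the partner's age is not restricted.

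These arguments narrow the point without removing it. None of them supplies a stated duty to notify on Days 29–90.

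**Conclusion.** The point holds in a limited form. For men under the 90-day rule, a partner pregnancy that begins on Days 29–90 after the last dose (62 days) is not clearly required to be notified or followed to outcome, and the Week 82 visit does not cover that period. This is a minor drafting inconsistency in safety reporting. It affects no efficacy endpoint, significance level, power or planned analysis, and few events are expected.

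The conclusion rests on two assumptions: that no sponsor document outside the protocol and SAP already sets a longer reporting period for partners, and that the man has not moved into the extension study. The visit calculation applies to men who complete treatment at Week 78. Men who stop drug early may be seen at later off-drug visits, but attendance at those is encouraged rather than required.

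**What to change.** Reconcile criterion 19 (including its reference to criterion 18 for partners), Section 8.1.2 and Section 8.4.3. The reporting period for a partner's pregnancy should be stated once and should match the male contraception period. The same text should say whether Section 8.1.2 stands on its own or is limited by Section 8.4.3, and how men vasectomized 6 months or more before first dose are treated. The sponsor's medical and safety staff decide which period applies; this review takes no view on that.

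One sentence in an amendment or a safety-reporting instruction is enough. SAP Section 4.1 reports that enrollment is complete with 325 randomized, and the protocol synopsis estimates last-subject completion in August 2024, so an instruction to sites is the more practical route. The downside is possibly one later contact with a few male subjects after Week 82.
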